7.4.3 Clinical Laboratory Assessments

Where applicable, abnormal laboratory results will be graded according to NCI CTCAE v4.0. A shift table, presenting the 2-way frequency tabulation for baseline and the worst post-baseline value according to the NCI CTCAE grade, will be provided for selected clinical laboratory tests. Both scheduled and unscheduled post-baseline values will be considered.

For Part A, descriptive statistics will be provided for clinical laboratory data for actual results, changes from baseline, and relative to the upper limit of normal range (ULN) over time by pooled placebo and ascending ALN-GO1 dose.

For Part B, descriptive statistics will be provided for clinical laboratory data for actual results, changes from baseline and relative to the upper limit of normal range over time according to the data display specification in Section 7.2.

Clinical laboratory tests with normal ranges will be classified as Low, Normal, and High. For these tests, abnormal values will be flagged in the listings with H when the value is higher than the upper limit of the reference ranges and with L when the value is lower than the lower limit of the reference ranges.

This categorical data will also be summarized in shift tables comparing the worst value post-baseline with those at the baseline visit. When there are both high and low abnormal values for a subject for a particular laboratory variable, the worst value will be taken (the value furthest outside of the normal ranges, or the first value experienced, if this value is the same). In Part A, frequencies and percentages will be presented by dose group. In Part B, shift table will be

summarized by pooled placebo and ascending single-blind ALN-GO1 dose and by ALN-GO1 dose in single-blind and open-label combined.

All clinical laboratory data in Part A and Part B will be listed.

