7.4.1 Adverse Events

In Part A, summary tables for AEs will be presented by ascending ALN-GO1 dose level, in total with all subjects receiving ALN-GO1, and placebo with subjects/patients receiving placebo pooled across enrollment cohorts presented first. AEs will be summarized separately for the single-blind dosing period and the study.

In Part B, for patients who were randomized to placebo, an AE during the single-blind period is defined as an AE with onset date/time on and after the first dose date/time of placebo and prior to the first dose date/time of open-label ALN-GO1. For patients who were initially randomized to ALN-GO1 a AE during the single-blind period is defined as an AE with onset date/time on or after the first dose date/time of ALN-GO1 and up to, and including, Study Day 85. AEs for single-blind period will be summarized by regimen and ascending dose level of ALN-GO1 and pooled placebo across regimen and dose being presented first. Sub-total for each regimen and overall will also be presented.

In Part B, a summary of AEs for the single-blind period will be provided by regimen and ascending dose level of ALN-GO1 and pooled placebo presented first. Total for each regimen and overall of ALN-GO1 will also be provided.

In Part B, for all patients receiving ALN-GO1, either as single-blind or open-label administration, and in any sequence, a AE is defined as an AE with onset date/time on or after the first dose date/time of ALN-GO1 and up to the end of study. All AEs under ALN-GO1 will be summarized by regimen and ascending dose, sub-total for each regimen, and for overall. At each dose level and for the sub-total and overall, AEs with be summarized for patients with single-blind administration only and then for single-blind and open-label administration combined.

In each analysis above, an overview of adverse events will be provided which summarizes subject-level incidence (frequency) of all AEs, drug-related AEs, grade 3/4/5 AEs, drug-related grade 3/4/5 AEs, treatment-emergent SAEs, drug-related treatment-emergent SAEs, and AEs leading to discontinuation of study drug and/or deaths.

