7.4.2 Dosing and Extent of Exposure

The actual dose administered and the number of injections will be summarized descriptively by dose level (or placebo) and overall for the Safety Analysis Set in Part A. Compliance with study drug administration is not relevant as all doses will be administered by qualified clinical study site personnel and recorded on the electronic Case Report Form.

Part B consists of three doses of study drug on Days 1, 29, and 57 for monthly dosing cohorts. For patients who randomized to placebo and crossed over to ALN-GO1 during the open label portion, study drug will be administered on Days 85, 113, and 141. Patients who randomized to receive ALN-GO1 will receive study treatment in a single-blind manner while patients enrolled in expansion cohorts will receive ALN-GO1 in an open-label manner.

In Part B for quarterly dosing cohorts, patients will receive either ALN-GO1 or placebo according to the randomized treatment assignment on Day 1. All patients in quarterly dosing cohorts, including those randomized to placebo, will receive open-label ALN-GO1 on Day 85 at the same dose administered to the cohort into which they were initially randomized.

Treatment duration of study drug in Part B is defined as:

- For patients randomized to placebo in monthly or quarterly cohorts, treatment duration of placebo is min (first dose date of open-label ALN-GO1 or visit date of Day 85 visit) – first dose date of placebo +1
- For patients in monthly dosing regimen, treatment duration of ALN-GO1 is the visit date of Day 85 relative to first dose of ALN-GO1 first dose date of ALN-GO1 +1
- For patients randomized to placebo in quarterly dosing cohorts, their treatment duration of open-label ALN-GO1 is the same as for monthly dosing regimen.

• For patients randomized to ALN-GO1 in quarterly dosing cohorts, the single-blind treatment duration is Day 85 visit date – first dosed date of ALN-GO1 +1 and the total ALN-GO1 treatment duration is Day 169 visit date – first dose date of ALN-GO1 +1.

Treatment duration of study drug will be summarized using descriptive statistics by regimen, ascending dose level of ALN-GO1, pooled placebo, and in total for the single-blind time period and total ALN-GO1 dosing period.

In Part B, dosing status will be tabulated by regimen and dose level (including placebo during the summary for the single-blind study period). The following categories will be summarized:

- Subjects with a missed dose,

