7.4.6 ECGs

Analyses of ECGs for both Part A and Part B and will be based on the Safety Analysis Sets.

In Part A, analyses will be presented separately for the single-blind dosing period and safety and PD follow-up period. In Part B, analyses will be presented separately for the single-blind dosing period (by pooled placebo, regimen, and ascending ALN-GO1 dose), ALN-GO1 dosing period (by regimen and ascending ALN-GO1 dose, regardless of treatment sequence), quarterly open-label ALN-GO1 dosing period (by ascending ALN-GO1 dose), postdose follow-up period (by ascending ALN-GO1 dose), and Safety and PD follow-up period (by regimen and ascending ALN-GO1 dose, regardless of treatment sequence).

Subjects with the following diagnoses or abnormal ECG findings will be excluded from the ECG analysis: artificial pacemaker (recorded as presence of atrial pacing, ventricular pacing, and/or atrial ventricular pacing), atrial fibrillation (or flutter), left bundle branch block (complete or incomplete), and right bundle branch block (complete or incomplete).

The number and percentage of patients with normal, abnormal, and clinically significant abnormal results at baseline and each timepoint will be summarized.

For both Part A and Part B, electrocardiogram parameters (ventricular rate, PR, QRS, QT, QT_cB, and QT_cF) will be summarized using descriptive statistics for actual values and for changes from baseline by scheduled time of evaluation (given in the Schedule of Assessments). These summaries will be presented separately for the time periods in Sections 7.1 (Part A) and Sections 7.2.1-2 (Part B).

Baseline, post baseline maximum QTcF, and post baseline maximum change from baseline in QTcF during the study will be summarized with descriptive statistics. The incidence of notable ECG changes from baseline in maximum absolute QT, QTcF, and QTcB intervals (<=450, > 450, > 480, and > 500 ms) over all post-treatment evaluations, as well as in QT, QTcF, and QTcB maximum changes from baseline (> 30 and > 60 ms) over all post-treatment evaluations will be summarized by dose level of ALN-GO1, pooled placebo, and overall for all subjects receiving ALN-GO1 in Part A. In Part B, the summary will be presented by regimen and ascending ALN-GO1 dose level, regardless of treatment sequence.

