7.6 Pharmacodynamic and Exploratory Analyses

Pharmacodynamic parameters will be measured from blood and urine samples collected at times outlined in the Schedule of Assessments in both Part A and Part B. PD analyses will be based on the Pharmacodynamic Analysis Sets.

24-hour urine oxalate content corrected for BSA will be calculated as:

[24-hour urine oxalate in mmol/L]*[24-hour urine volume recorded in CRF in ml] /(1000 ml per L)*24hours/[actual collection time calculated from CRF in hours] *1.73/[patient BSA]

Where patient BSA will be calculated as:

Patient BSA = sqrt([mean height in cm] *[weight in kg]/3600).

24-hour urine creatinine clearance corrected for BSA will be calculated as:

[24-hour urine creatinine concentration in mg/dl]*[24-hour urine volume recorded in CRF in ml]

/[Plasma creatinine in mg/dl]/[actual collection time calculated from CRF in minutes] *1.73/[patient BSA]24-hour urine oxalate/creatinine ratio will be calculated as:

24-hour urine oxalate concentration (mg/L) /24-hour urine creatinine concentration (mg/dL)/10.

For Part A and Part B, the mean and standard error of actual values and changes from baseline in plasma and urine glycolate will be plotted over time by ALN-GO1 dose level and placebo. In

addition, plots will be provided for plasma and urine glycolate of individual subjects by dose level of ALN-GO1 and placebo.

For Part B, the mean and standard error of actual values and changes from baseline in urinary oxalate per 24-hour urine collection and urinary creatinine per 24-hour urine collection will be plotted over time. In addition, the plots will be presented separately by ADA status. Plasma glycolate concentration and oxalate/creatinine ratio will be plotted in the same manner. For patients randomized to placebo, figures will include PD measurements up to the first dose of open-label study drug.

For other PD variables in Part A and B, descriptive statistics will be provided for actual results, change from baseline, and percent change from baseline. For Part B, the PD summaries will be presented according to the data display specification in Section 7.2.3.For Part A and Part B, Cmax and AUCt of plasma glycolate will be presented with descriptive statistics and percent coefficient of variation [%CV]) by regimen and ascending dose level and placebo presented first.

In Part A and Part B, all PD data will be listed by regimen, dose, ADA status (Part B only) and subject/patient.

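### Part A follow-up after Day 57 depends on glycolate recovery, but the worst-value lab shifts have no common window, and several related outputs leave the window or the follow-up time unstated

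*SAP*

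**What the plan says.** **Follow-up rule.** Protocol 4.1.1 and SAP 3.1.1 keep Part A subjects in follow-up for at least 57 days, and then until plasma glycolate is no more than 20% above baseline or is within the upper limit of normal (14 nmol/mL). Protocol Table 1 repeats clinical laboratory tests, ECGs and PD blood samples at every 28-day visit after Day 57. SAP 6.1.1 records AEs to the end of study. SAP 7.1 treats anything after Day 57 as a separate safety and PD follow-up period.

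**Lab shifts (SAP 7.4.3).** For the CTCAE-grade shift table: "Both scheduled and unscheduled post-baseline values will be considered". For the low/normal/high classification: "This categorical data will also be summarized in shift tables comparing the worst value post-baseline with those at the baseline visit". Part A is shown by dose group. No window is given.

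**ECG (SAP 7.4.6).** The section opens with a split: "In Part A, analyses will be presented separately for the single-blind dosing period and safety and PD follow-up period". It then specifies that "post baseline maximum change from baseline in QTcF during the study will be summarized with descriptive statistics", and that the QT, QTcF and QTcB categories "over all post-treatment evaluations will be summarized by dose level of ALN-GO1, pooled placebo, and overall".

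**AEs and exposure.** SAP 7.4.1, for Part A: "AEs will be summarized separately for the single-blind dosing period and the study". SAP 7.4.2 limits Part A exposure to dosing: "The actual dose administered and the number of injections will be summarized descriptively by dose level (or placebo) and overall".

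**Glycolate (SAP 7.6).** "Cmax and AUCt of plasma glycolate will be presented with descriptive statistics and percent coefficient of variation", by dose with placebo first; t is not defined. Means with standard errors are plotted over time with no last visit stated for Part A. SAP 4.3.4 uses recorded values only.

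**The concern.** Protocol 1.2.2 names plasma glycolate as a marker of drug activity. A rule that ends observation when glycolate recovers therefore makes the length of observation a consequence of treatment. Placebo subjects, and those on doses with little PD effect, should mostly finish at about Day 57, while subjects on PD-active doses stay.

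Any statistic of the form worst value, maximum or at least one event tends to rise with the number of looks. Comparing it across groups observed for different lengths of time mixes a drug effect with a follow-up effect. Safety is the primary objective, and each Part A cohort has only 6 active subjects (8 at 3:1), so one chance shift moves a cohort's percentage by 1/6, or 17 points. The lab shift tables are the clearest case, because nothing in SAP 7.4.3 limits them to a common window and no Part A table shows how long each group was followed.

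Late glycolate means have a related problem. They can suggest that the PD effect lasts longer than it does in the cohort as a whole.

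**Working it through.** The documents contain no power or event figure to reproduce. The planned Part A number does reproduce: (3 + 2) cohorts × 8 = 40, of whom 30 are active and 10 placebo.

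**1. What the documents fix or imply**
- Longest postdose follow-up (Protocol 4.2): 405 − 45 days of screening = 360 days. This is an estimate, not a cap. 360/57 = 6.3.
- 28-day visits after Day 57 and within 360 days: Days 85, 113, …, 337, which is 10 visits.
- Postdose lab visits (Protocol Table 1): Days 2, 8, 15, 29, 43 and 57 = 6. To Day 169: 6 + 4 = 10. To Day 337: 6 + 10 = 16.
- Postdose ECG time points: 4 on Day 1 plus Days 2, 29 and 57 = 7. To Day 169: 11. To Day 337: 17.

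Everything below rests on assumed rates or curves, with no drug effect on safety.

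**2. Lab shifts.** With independent visits and a chance p of an abnormal value per visit, P(at least one) = 1 − (1 − p)^k.

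| p | k = 6 (Day 57) | k = 10 (Day 169) | k = 16 (Day 337) |
|---|---|---|---|
| 1% | 5.9% | 9.6% | 14.9% |
| 2.5% | 14.1% | 22.4% | 33.3% |
| 5% | 26.5% | 40.1% | 56.0% |

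Repeat values in one subject are correlated. A simulation with a 95% reference range, baseline in range and an equal correlation of 0.7 down to 0.3 between visits gives 14–23% to Day 57, 18–34% to Day 169 and 23–47% to Day 337. In a group of 6 all followed to Day 169, that is 6 × (0.183 − 0.136) = 0.3 to 6 × (0.342 − 0.234) = 0.65 extra subjects per analyte. This sizes the low/normal/high table only, not the CTCAE-grade table.

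**3. QTcF maximum change.** Simulated with a between-day SD of 6–10 ms, a within-day SD of 4–6 ms and one shared baseline. The mean maximum is 9–14 ms over 7 time points, 11–18 ms over 11 and 13–20 ms over 17. The share above 30 ms is 0.5–9%, 1–15% and 2–21%.

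**4. Whole-study AEs.** Assume 30% incidence by Day 57 and a later hazard k times the earlier one. Incidence by Day 169 = 1 − 0.7^(1 + k × 112/57), which is 41% for k = 0.25 and 65% for k = 1.

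**5. Glycolate AUCt, only if t is the last sample.** At a constant level, AUC from Day 1 relative to Day 57 is 84/56 = 1.5 (Day 85), 112/56 = 2.0 (Day 113), 168/56 = 3.0 (Day 169) and 336/56 = 6.0 (Day 337). Example: glycolate at twice baseline to Day 57, then falling linearly to 1.2 times by Day 169. Relative to placebo at 1.0 times to Day 57, the ratio is (2 × 56)/56 = 2.0 on a common Day 57 window, but (112 + 112 × 1.6)/56 = 5.2 if each AUC runs to the subject's last visit.

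**6. Late plasma glycolate means.** Suppose those still followed average 60–100% above baseline and leavers stay at or below 20%.
- 3 of 6 followed: whole-cohort mean at most (3 × 60 + 3 × 20)/6 = 40% to (3 × 100 + 3 × 20)/6 = 60%. The plotted mean is 1.5–1.7 times that.
- 5 of 6 followed: (5 × 60 + 20)/6 = 53.3% to (5 × 100 + 20)/6 = 86.7%; 1.1–1.2 times.
- 6 of 6 followed: no bias.

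Subjects who leave through the 14 nmol/mL limit may still be more than 20% above baseline, which narrows the gap.

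**The case against.** Several stronger readings are tempting, and the documents do not support them.

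- **That QT maxima lack any Day 57 version.** SAP 7.4.6 opens by splitting Part A ECG analyses by period. The defect is a conflict between that sentence and the later wording, which a programmer cannot settle without a ruling.
- **That AUCt accumulates over unequal time.** The SAP does not say so. It leaves t undefined, and the ratios in step 5 apply only to one possible reading.
- **That late means contain only unrecovered subjects.** A visit mean covers those not recovered at the previous visit, so each subject's recovery value is included. As extracted, Protocol Table 1 shows no Part A urine PD sampling after Day 57, so the point concerns plasma only.
- **That the AE comparison itself is compromised.** AEs are the primary endpoint and already have a single-blind-period table, which SAP 7.1 in effect ends at Day 57. Only the whole-study table lacks follow-up time.
- **That the same criticism carries over to Part B.** Part B patients can leave for the extension study without recovering, so the selection differs, and it is not argued here.

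The general defence has weight too. By-visit lab summaries give a common-schedule comparison to Day 57, n is reported, individual glycolate plots and full listings are planned, and Protocol 8.2.7 itself asks for shifts to the worst post-baseline value. Table formats are left to a programming specification that is not available here and may set windows. No hypothesis is tested, and Part A escalation rests on committee review of at least 48 hours of safety data.

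This limits the consequence. It does not supply a common window for the worst-value lab tables or any follow-up time by group. By-visit tables and listings do not correct a worst-value statistic.

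**Conclusion.** The point holds as a cheap improvement. Its firm core is that Part A observation beyond Day 57 depends on treatment, that the worst-value lab shifts are taken without a common window, and that no Part A follow-up time is reported. Active doses can then look worse than placebo with no drug effect on safety. The QT window is internally inconsistent, t in AUCt needs a definition, and late plasma glycolate means can overstate persistence.

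The documents give the visit counts (6 lab visits to Day 57, up to 16 by Day 337) and imply an estimated maximum of about 360 days postdose. Every percentage or ratio beyond these rests on the stated assumptions. Recovery times are not given, so the real effect may be small if most subjects recover by about Day 57. The harm is limited to interpretation of the final report.

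**What to change.** 1. **SAP 7.1:** state that the Part A single-blind period ends at Day 57. Section 7.1 only implies this, and Protocol Table 1 separates a dosing period from a postdose follow-up period.
2. **SAP 7.4.3:** add Part A worst-lab-shift tables through Day 57 as the comparison with placebo. Keep the whole-study tables so that late safety values still appear.
3. **SAP 7.4.6:** state that the Part A QT, QTcF and QTcB maximum and category tables are given through Day 57 as well as over the whole study.
4. **SAP 7.4.2:** add a Part A follow-up-time summary by dose and pooled placebo, shown beside the whole-study tables.
5. **SAP 7.6:** set t to Day 57 for the Part A plasma glycolate AUCt comparison with placebo.
6. **SAP 7.6:** print the number still followed at each Part A plasma glycolate mean after Day 57, and read those points with the individual profiles already planned. The means need not stop at Day 57, since that would discard information on duration.

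The cost is SAP text, a few extra Part A tables and one follow-up summary, all from data already collected. Nothing planned is removed.

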1.5. Benefit-Risk Assessment

ALN-GO1 is designed to reduce hepatic production of oxalate. The potential benefit of this treatment is the amelioration of the clinical course of PH1 in patients across the spectrum of disease, irrespective of age and disease stage; however, patients with PH1 in this study may not receive treatment for a sufficient duration, or at an adequate dose, to experience clinical benefit. There is no benefit for healthy subjects participating in this clinical study of ALN-GO1. The potential risks of ALN-GO1 include pathway- and disease-specific risks, and non-specific, off-target risks.

Reduction of GO is expected to lead to reduction in hepatic oxalate production at the expense of increased glycolate, an organic acid. Therefore, study drug-induced increases in plasma and urine glycolate levels are anticipated in both healthy subjects and patients administered ALN-GO1. Since elevated levels of this organic acid are expected to be readily buffered, and its high solubility is not expected to result in crystallization in the urinary tract, the potential risk of increased glycolate production is considered low. Importantly, no toxicity has been observed in NHP pharmacology and toxicology studies, where profound suppression of hepatic GO, with associated increases in plasma glycolate levels, has been demonstrated. In particular,

maintenance of normal serum bicarbonate levels in these animals indicates that there is no evidence of acidosis. Finally, a recent clinical case study described a child with an incidentally discovered homozygous defect in HAO1, the gene encoding GO. The patient exhibited marked elevations of urine glycolate, but no associated metabolic abnormalities and normal renal and hepatic function.[9]

The potential negative consequences of ALN-GO1 administration to patients with impaired renal function, including those with end stage renal disease (ESRD), are considered low. ALN-GO1, in common with other Sponsor-developed RNAi compounds, is conjugated to N-acetyl galactosamine (GalNAc) to enable rapid and specific uptake by hepatocytes via the asialoglycoprotein receptor. Clinically effective doses of ALN-GO1 are not expected to saturate this receptor-mediated uptake or to result in enhanced extra-hepatic uptake or significant extra-hepatic exposure via accumulation; however, only patients with relatively well-preserved renal function are eligible to participate in this study.

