8.2.7. Safety Analyses

The primary safety parameter is the incidence of AEs. Safety will also be evaluated through vital signs, ECGs, clinical laboratory assessments, and physical examinations; Echo assessments will be evaluated in Part B only. ADAs will also be analyzed.

AEs will be summarized by the MedDRA System Organ Class and Preferred Term (Version 16, or higher). Prior and concomitant medications will be classified according to the World Health Organization (WHO) drug dictionary.

Separate tabulations of the incidence of treatment emergent adverse events (TEAEs), TEAEs by maximum severity, treatment-related AEs, SAEs, and discontinuation due to AEs will be provided. By-subject listings will also be provided for any deaths, SAEs and AEs leading to discontinuation.

Descriptive statistics will be provided for clinical laboratory data and vital signs data, presented as both actual values and changes from baseline over time. Clinical laboratory assessment shift tables from baseline to worst post-values will be presented. Abnormal physical examination findings, ECG, and Echo (Part B only) data will be presented in a by-patient data listing.

Descriptive statistics will be provided for ECG interval data and presented as both actual values and changes from baseline relative to each on-study evaluation and to the last evaluation on study. Details of any abnormalities will be included in patient listings.

ADA results will be provided in a by-patient data listing.

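### The Low/Normal/High laboratory shift table counts a subject with both low and high values of one test in one direction only, on a distance scale the SAP does not define

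*SAP*

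**What the plan says.** SAP 7.4.3 plans two laboratory shift tables.

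- **By CTCAE grade.** It shows baseline against "the worst post-baseline value according to the NCI CTCAE grade, will be provided for selected clinical laboratory tests". The tests are not named, and nothing is said about how low and high grades of one test are combined.
- **By Low, Normal and High.** "This categorical data will also be summarized in shift tables comparing the worst value post-baseline with those at the baseline visit".

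The selection rule belongs to the second table. Its trigger is narrow: "When there are both high and low abnormal values for a subject for a particular laboratory variable". In that case "the worst value will be taken (the value furthest outside of the normal ranges"), with a tie going to whichever value came first.

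Protocol 8.2.7 is less specific: "Clinical laboratory assessment shift tables from baseline to worst post-values will be presented".

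The same SAP section flags out-of-range values in the listings, including "with L when the value is lower than the lower limit of the reference ranges", and lists all laboratory data. Its by-visit summaries cover actual values, changes from baseline and values relative to the upper limit of normal. SAP 4.3 adds the minimum and maximum to the descriptive statistics.

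**The concern.** A low and a high value of the same test can be different safety events. SAP 6.1.7 includes potassium, calcium, glucose and bicarbonate, for which neither direction is simply a worse form of the other. Ranking them by distance from the range is not a clinical ranking, and without a stated scale two programmers could build different tables from the same data.

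Laboratory assessments support the primary safety objective, and no other planned summary clearly restores the lost count. The by-visit summaries are set against the upper limit only. A by-visit minimum does not give the number of subjects below the lower limit or their baseline category. The CTCAE table covers an unnamed subset of tests.

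**Working it through.** The plan states no figure on this point, and SAP 4.1 gives no power basis for the sample size, so there is nothing to reproduce. Three checks were made.

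**1. What the rule does.** The documents give no bicarbonate range, so 22 to 29 mmol/L is assumed. Four readings of the distance rule were applied: raw distance, distance divided by the breached limit, absolute log-ratio to that limit, and distance divided by the range width (29 − 22 = 7).

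| Post-baseline values | Raw | Relative to limit | Log-ratio | Range width |
|---|---|---|---|---|
| 19 and 33 | 3 v 4: High | 0.136 v 0.138: High | 0.147 v 0.129: Low | 0.429 v 0.571: High |
| 19 and 32.5 | 3 v 3.5: High | 0.136 v 0.121: Low | 0.147 v 0.114: Low | 0.429 v 0.500: High |
| 18 and 32 | 4 v 3: Low | 0.182 v 0.103: Low | 0.201 v 0.098: Low | 0.571 v 0.429: Low |
| 19 and 32 | 3 v 3: tie | 0.136 v 0.103: Low | 0.147 v 0.098: Low | 0.429 v 0.429: tie |
| 19 and 27 | Low | Low | Low | Low |

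In the first two rows the category depends on the reading. In the third the high value is the one dropped, so the loss runs both ways. In the fourth, under two of the readings, collection order decides. In the last row there is no high value, so nothing is lost.

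**2. Weight of one subject.**
- Part A: 8 per cohort at 3:1 gives 8 × 3/4 = 6 on ALN-GO1, and 1/6 = 16.7 percentage points.
- Part B single-blind: 4 per cohort at 3:1 gives 3 on ALN-GO1, and 1/3 = 33.3 points.
- Part B combined monthly groups (N = 4 or 8 in SAP 7.2.3): 25.0 or 12.5 points.

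**3. How often both directions might occur by chance.** From the protocol: up to 40 subjects and 24 patients; 6 post-dose laboratory visits in Part A (Table 1, to Day 57) and 8 in Part B monthly dosing (Table 2, to Day 141). Assumed: 2.5% of values beyond each limit at each visit, and about 20 two-sided tests.

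For independent visits, P(at least one low and one high in k visits) = 1 − 2(0.975^k) + 0.95^k.
- k = 6: 0.0170
- k = 8: 0.0301

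Expected pairs = 40 × 20 × 0.0170 + 24 × 20 × 0.0301 = 13.6 + 14.5 = about 28, out of 64 × 20 = 1,280 subject-by-test cells (2.2%).

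If Part B is cut at Day 85 it also has 6 visits, and the total is 1,280 × 0.0170 = about 22.

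Independence is the extreme assumption. With normally distributed values, the same marginal rates and the original 6 and 8 visits, an equal correlation between a subject's visits gives about 3 pairs at 0.3 and about 0.2 at 0.5.

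**The case against.** The strongest reply is that little is lost. The study is descriptive, with no hypothesis tests, and no decision rule uses this table. Every low value is flagged and listed, and by-visit minima are shown. Protocol 7.5.7.2 requires clinically relevant laboratory findings to be recorded as adverse events, and Protocol 7.5.6 asks for unexplained, clinically relevant abnormal tests to be repeated and followed. The Safety Review Committee sees unblinded data throughout. With three to eight patients in a Part B dose group, listings can be read directly. A single worst value also agrees with Protocol 8.2.7, and the programming specification mentioned in SAP 8.2 may define the scale.

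Most of this stands and sets the severity. It does not repair the table, which reports an incomplete count under an undefined rule; a reader would have to recover the count by hand.

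Three stronger readings are tempting, and the documents do not support them.

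- **That low values disappear from the report.** They are uncounted in one table only, and only when the same subject also has a high value of that test that is judged further out or, on a tie, came first. High values are lost in the same way.
- **That the rule hides an acidosis signal.** Protocol 1.5 says "maintenance of normal serum bicarbonate levels in these animals indicates that there is no evidence of acidosis", which concerns animals; neither document designates bicarbonate as a signal for this trial. A subject with only low bicarbonate is counted as Low, and a drug effect that lowers bicarbonate makes a larger high excursion in the same subject less likely.
- **That the SAP prescribes raw distance.** Raw distance is a natural reading, but the text names no scale.

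**Conclusion.** The point holds for the Low/Normal/High shift table of SAP 7.4.3. When one subject has both directions on one test, one abnormality is left out of the count, and which one can depend on an unstated scale or on collection order. The number affected is probably small. The range of near 0 to about 28 pairs rests on assumed out-of-range rates, an assumed 20 tests, maximum enrolment and an unknown within-subject correlation. It describes chance variation only, without disease, treatment or illness effects and without unscheduled or later visits. The case rests on the rule and the small groups, not on the upper figure. Severity is minor: no data are lost and no figure in the documents is wrong.

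**What to change.** In SAP 7.4.3, for two-sided tests, replace the single-value rule with two shifts: baseline category to the lowest post-baseline value, and baseline category to the highest. A subject may then count in both; the pair 19 and 33 above would count once as Low and once as High. List which tests are treated as two-sided, and name the tests in the CTCAE-grade table. The distance scale and the tie rule are then no longer needed for two-sided tests. If a single worst value is kept instead, state the scale.

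The cost is SAP wording and one extra table shell before database lock. No new data are needed, and the change is compatible with Protocol 8.2.7. Label: free improvement.
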